#### 6.4.4.2 Multivariate display of immunogenicity endpoints

Data visualization techniques may be used to explore the relationship among immunogenicity readouts. The set of readouts may be based on 1 of the primary endpoints (eg, ICS), on the set of primary endpoints, or on immunogenicity endpoints that also include secondary or exploratory endpoints. To understand the relationship between pairs of readouts, scatter plots may be used when the number of readouts is small or for a larger number of readouts, a heat map showing the degree of correlation between any 2 pairs. Principal component analysis (PCA) and associated “biplots” of the scores and loadings are particularly useful to understand associations between readouts, especially when readouts are correlated [38]. PCA is a method to reduce the dimensionality of the number of readouts to a smaller set of values (principal components) that are normalized linear combinations of the readouts in such a way that the first principal component accounts for the most variability in the data and subsequent components, while maximizing variability, are uncorrelated with each other. A ‘biplot’ displays the first and second principal component scores and principal component loadings. The x-axis is the value from the first principal component and the y-axis is the second principal component, where each axis label includes the percentage of variation in the total set of readouts captured by the principal component. The top axis is the first principal component loadings and the right axis is the second principal component loadings. An arrow is drawn for each immunogenicity readout (eg, Env-specific CD4+ T cell polyfunctionality score, Env-specific CD8+ T cell total magnitude) from the origin to the point defined by its first 2 principal component loadings. The length of the arrow represents the amount of total variation of the set of readouts captured by the given readout. The direction of an arrow conveys the extent to which the variation of a readout is in the direction of the first or second principal component. The angle between 2 arrows conveys information about the correlation of the 2 readouts, with a 0 degree angle denoting perfect correlation and a 90 degree angle denoting no correlation. Each arrow on the biplot is labeled by the immunogenicity readout it represents. A biplot is annotated with key meta-information such as the treatment arm (most common application) or a demographic category. Depending on the application, K-means clustering and hierarchical clustering may also be applied for multivariate graphical display of immunogenicity readouts.

#### 6.4.4.3 Secondary analysis of binding antibody data as measured by the BAMA assay

When a small panel of antigens (eg,  $\leq 5$ ) is being assessed in a multiplexed immunoassay, the response magnitudes and rates at 2 weeks following the first and third vaccinations will be evaluated for each antigen. When a larger panel is being assessed, in addition to assessing each antigen separately, a summary measure across a group of similar antigens will be calculated, for example, a weighted-average may be constructed to account for the correlations between antigens as an integrated magnitude of responses to multiple antigens. Then this summary measure may be used as the outcome variable to assess if this overall response measure differs by arms.

#### 6.4.4.4 Secondary analysis of CD4+ and CD8+ T-cell response as measured by the ICS assay

The analysis of CD4+ and CD8+ T-cell response rates as measured by the ICS assay will be evaluated and compared as described under the general approach. For each T-cell subset, the positivity call for each peptide pool will include a multiple comparison adjustment for the number of peptide pools used in the assay. In general, the Mixture Models for Single-cell Assays (MIMOSA) statistical framework [39] and/or the Fisher's exact test-based positivity criteria will be used. Details of the positivity criteria will be discussed in the SAP. The magnitude of marginal response will be analyzed as described for quantitative data in the general approach section. For each T-cell subset, graphs will be used to display the background-subtracted magnitudes for each participant by protein, treatment arm, and timepoint. When 3 or more cytokines are being measured by the ICS assay, the polyfunctionality of ICS responses may also be analyzed as an exploratory endpoint. Besides descriptive plots of the magnitude of polyfunctional responses, the Combinatorial Polyfunctionality analysis of Antigen-Specific T-cell Subsets () statistical framework [40] may also be used to perform joint modelling of multiple T-cell subsets of different cytokine combinations. For example, the functionality score (FS) and the polyfunctionality score (PFS) may be used to summarize the multi-parameter ICS responses.

#### 6.4.5 Analyses prior to end of scheduled follow-up visits

Any analyses conducted prior to the end of the scheduled follow-up visits should not compromise the integrity of the trial in terms of participant retention or safety or immunogenicity endpoint assessments. In particular, early unblinded analyses by treatment assignment require careful consideration and should be made available on a need to know basis only.

##### 6.4.5.1 Safety

During the course of the trial, unblinded analyses of safety data will be prepared approximately every 4 months for review by the SMB. Ad hoc safety reports may also be prepared for SMB review at the request of the HVTN 122 PSRT. The HVTN leadership must approve any other requests for unblinded safety data prior to the end of the scheduled follow-up visits.

##### 6.4.5.2 Immunogenicity

An unblinded statistical analysis by treatment assignment of a primary immunogenicity endpoint may be performed when all participants have completed the corresponding primary immunogenicity visit and data are available for analysis from at least 80% of these participants. Similarly, an unblinded statistical analysis by treatment assignment of a secondary or exploratory immunogenicity endpoint may be performed when all participants have completed the corresponding immunogenicity visit and data are available for analysis from at least 80% of these participants. However, such analyses for a secondary or exploratory immunogenicity endpoint will only take place after at

least 1 of the primary immunogenicity endpoints of the same class (humoral or cell-mediated) or, if no primary endpoint of the same class, at least 1 of the primary immunogenicity endpoints reaches the aforementioned threshold. The Laboratory Program will review the analysis report prior to distribution to the protocol chairs, DAIDS, vaccine developer, and other key HVTN members and investigators. Distribution of reports will be limited to those with a need to know for the purpose of informing future trial-related decisions. The HVTN leadership must approve any other requests for HVTN immunogenicity analyses prior to the end of the scheduled follow-up visits.

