## 6.3 Blinding

Participants and site staff (except for site pharmacists) will be blinded as to participant treatment arm assignments (eg, vaccine or control). Study product assignments are accessible to those HVTN CRS pharmacists, DAIDS protocol pharmacists and contract monitors, and SDMC staff who are required to know

this information in order to ensure proper trial conduct. Any discussion of study product assignment between pharmacy staff and any other HVTN CRS staff is prohibited. The HVTN SMB members also are unblinded to treatment assignment in order to conduct review of trial safety.

When a participant leaves the trial prior to study completion, the participant will be told he or she must wait until all participants are unblinded to learn his or her treatment assignment.

Emergency unblinding decisions will be made by the site investigator. If time permits, the HVTN 122 PSRT should be consulted before emergency unblinding occurs. See the HVTN MOP for more information.

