## **11 Safety monitoring and safety review**

### **11.1 Safety monitoring and oversight**

#### **11.1.1 HVTN 122 PSRT**

The HVTN 122 PSRT is composed of the following members:

- DAIDS medical officer representative,
- Protocol chair and cochair,
- Protocol Team leader,
- Core medical monitor, and
- Clinical safety specialist.

The clinician members of HVTN 122 PSRT are responsible for decisions related to participant safety.

The Protocol Team clinic coordinator, clinical data manager, vaccine developer representative, clinical trial manager, and others may also be included in HVTN 122 PSRT meetings.

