### 11.2.3 Expedited reporting of adverse events to DAIDS

Requirements, definitions and methods for expedited reporting of AEs are outlined in Version 2.0 (January 2010) of the *Manual for Expedited Reporting of Adverse Events to DAIDS* (DAIDS EAE Manual), which is available on the RSC website at <http://rsc.tech-res.com/clinical-research-sites/safety-reporting/manual>. The SAE Reporting Category will be used for this study.

The internet-based DAIDS Adverse Experience Reporting System (DAERS) must be used for expedited AE reporting to DAIDS. In the event of system outages or technical difficulties, expedited AE reports may be submitted via the DAIDS EAE Form. For questions about DAERS, please contact [[contact]](mailto:[contact]) or from within the DAERS application itself.

The study products for which expedited reporting are required are:

- gp145 C.6980 with aluminum hydroxide adjuvant

- placebo (Sodium Chloride for Injection, 0.9%)

The expedited reporting period for this study comprises the entire study period for each individual participant (from study enrolment until study completion or discontinuation from the study). During this period the SAE Reporting Category will be used.

After the protocol-defined AE reporting period for the study, unless otherwise noted, only Suspected, Unexpected Serious Adverse Reactions as defined in Version 2.0 of the DAIDS EAE Manual must be reported to DAIDS, if the study staff become aware of the events.

The NIAID/DAIDS will report all unexpected SAEs related to the study products observed in this clinical trial to the FDA in accordance with 21 CFR 312.32 (IND Safety Reports). However, because safety is a primary study endpoint, the Sponsor Medical Officer will not routinely be unblinded to study treatment assignment when there is an assessment of relatedness of the SAE with the study product(s); and the safety report will be sent to the FDA based on the blinded attribution assessment.

If the PSRT believes unblinding is appropriate (eg, if unblinding to treatment assignment will assist with the clinical management of the SAE), the PSRT will consult the independent HVTN SMB for a recommendation. In the event the HVTN SMB determines that unblinding is indicated, the SMB will inform the individual (eg, site physician) of the participant's treatment assignment in such a manner as to maintain the study blind of the PSRT and study team. For additional impact and management of SAEs on the study, see Section 11.4.

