2 OVERVIEW

The following describes the Statistical Analysis Plan (SAP) for the analysis of safety and immunogenicity data from HVTN 122 for Safety Monitoring Board (SMB) and Protocol Team immunogenicity data reports. As detailed in SCHARP SOP-0013, Revision 5 (effective date: August 15, 2016), this SAP is required prior to the first analysis of each respective data type and must be approved by the lead protocol statistician. The plan will be reviewed and updated prior to the first SMB report and the first PT report of each immunogenicity data type with all major revisions of the plan archived.

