12.2.1 List of Tables

- Response rate table by lab, isotype, antigen, visit, day, and group/treatment arm
- Listing of magnitudes (MFI*) among positive responders.
- Summary statistics (i.e., min, mean, median, max) among responders by lab, isotype, antigen, visit, day, and group/treatment arm.
- Summary statistics (i.e., min, mean, median, max) among all participants (positive and negative responders) by lab, isotype, antigen, visit, day, and group/treatment arm.
- Comparisons of response rates between treatment groups at each visit.
- Comparisons of response magnitudes among responders between treatment groups at each visit, if there are at least 5 responders within each group at a given visit.
- Comparisons of response rates between visits 4 and 9 for each treatment group.

- Comparisons of response magnitudes among responders between visits 4 and 9 for each treatment group if there are at least 5 responders at each visit within a given treatment group.

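### Unblinded immunogenicity reports allowed before follow-up ends have no limit on individual-level content, and their named recipients overlap with people who are to stay blinded

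*Protocol*

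**What the plan says.** **Early reports.** Protocol 6.4.5.2 and SAP 10.4.2 allow an unblinded immunogenicity analysis by treatment assignment once "all participants have completed the corresponding primary immunogenicity visit and data are available for analysis from at least 80% of these participants". The Laboratory Program reviews the report "prior to distribution to the protocol chairs, DAIDS, vaccine developer, and other key HVTN members and investigators". Two limits apply. "Distribution of reports will be limited to those with a need to know for the purpose of informing future trial-related decisions", and under Protocol 6.4.5 early analyses should not damage trial integrity, safety endpoint assessment included.

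**Who is blinded.** Protocol 6.3 states: "Participants and site staff (except for site pharmacists) will be blinded as to participant treatment arm assignments". It gives access to assignments to site pharmacists, DAIDS protocol pharmacists and contract monitors, SDMC staff who need it, and the SMB. Protocol 11.2.3 does not routinely unblind the Sponsor Medical Officer for related SAEs. When the SMB does unblind a single case, it must do so "in such a manner as to maintain the study blind of the PSRT and study team". Protocol 11.1.1 lists among the PSRT members a DAIDS medical officer and the "Protocol chair and cochair".

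**What the reports contain.** SAP 2 says the plan is "for Safety Monitoring Board (SMB) and Protocol Team immunogenicity data reports". SAP 12 then gives the contents by assay. There are responder listings for ICS (12.1.1), BAMA ("Listing of magnitudes (MFI*) among positive responders", 12.2.1) and neutralizing antibody (12.3.1). Spaghetti plots are planned for BAMA (12.2.2) and, if further visits are assayed, for the other two assays. SAP 10.5.3 adds per-participant ICS magnitudes by arm. No shorter version is defined for reports issued during follow-up.

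**The concern.** The protocol names chairs, DAIDS and investigators as recipients of unblinded reports, and elsewhere expects the PSRT, the study team and site staff to remain blind. No firewall between these roles is described. The need-to-know rule governs who may receive a report. It does not govern what the report shows, and its test (informing future trial-related decisions) does not exclude a chair or an investigator.

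AE severity and relationship to product are part of the safety endpoints in Protocol 5.1 and 5.2, and SAP 6 relies on the relationship as assessed by HVTN staff. An Env-antibody responder list that identifies participants would tell its readers, with high probability, who received vaccine. If those readers also attribute or review AEs, the later attributions are no longer reliably blinded.

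**Working it through.** The plan gives no figure on this point to reproduce. The check has three parts.

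**1. Recipients against blinded roles**

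| Named recipient (Protocol 6.4.5.2) | Overlapping role | Blinding statement |
|---|---|---|
| Protocol chairs | PSRT members (11.1.1) | PSRT and study team blind kept (11.2.3) |
| DAIDS | DAIDS medical officer on the PSRT (11.1.1) | Sponsor Medical Officer not routinely unblinded (11.2.3) |
| Investigators | Site staff, if site investigators are meant | Site staff blinded except pharmacists (6.3) |

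The first row is an overlap on the face of the text. The second and third depend on which DAIDS staff and which investigators receive the report, and the text leaves that open.

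**2. What a responder listing would reveal**

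Inputs: 40 vaccinees and 5 placebo recipients (Protocol 6.1). Prior chance of vaccine = 40/45 = 88.9%; of placebo = 5/45 = 11.1%. The documents give neither the vaccinee response rate *r* nor the placebo positive rate *f*, so both are assumed. The missing share *m* is taken as equal across arms: 10% is the protocol's planning figure (6.1), and 20% is the most the 80% trigger allows (0.80 × 45 = 36 participants with data).

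- P(vaccine given listed) = 40*r* / (40*r* + 5*f*); equal *m* cancels.
- P(placebo given unlisted) = 5[1 − (1 − *m*)*f*] / {5[1 − (1 − *m*)*f*] + 40[1 − (1 − *m*)*r*]}.

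| *r* | *f* | *m* | Vaccine, if listed | Placebo, if unlisted |
|---|---|---|---|---|
| 50% | 0% | 0% | 20/20 = 100% | 5/25 = 20.0% |
| 50% | 5% | 0% | 20/20.25 = 98.8% | 4.75/24.75 = 19.2% |
| 90% | 5% | 0% | 36/36.25 = 99.3% | 4.75/8.75 = 54.3% |
| 95% | 3% | 0% | 38/38.15 = 99.6% | 4.85/6.85 = 70.8% |
| 95% | 3% | 10% | 99.6% | 4.865/10.665 = 45.6% |
| 95% | 3% | 20% | 99.6% | 4.88/14.48 = 33.7% |
| 100% | 0% | 0% | 100% | 5/5 = 100% |

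Being listed nearly settles vaccine receipt, from a prior that is already high. Being unlisted is informative only if the response rate is high and few results are missing. Response status alone does not separate 300 mcg from 100 mcg.

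**3. How much follow-up remains**

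Total duration is 17 months and each participant is followed for 12 (Protocol 3), so accrual including the hold takes about 17 − 12 = 5 months, or 5 × 30.44 = 152 days. This treats the planned duration as achieved.

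- *Visit 9 report.* When the last enrollee reaches day 182, the first is at day 182 + 152 = 334. Remaining follow-up runs from 364 − 334 = 30 days to 364 − 182 = 182 days, before assay and analysis lag. The last vaccination is at day 168 and its 7-day reactogenicity period ends at day 175, so both are complete for everyone.
- *Visit 4 report.* When the last enrollee reaches day 14, the first is at day 166. The day 168 vaccination would still lie ahead for all, again before lag. The day 56 vaccination would lie ahead only for those enrolled within 56 − 14 = 42 days of the last participant: 42/152, about 28%, if accrual is uniform.

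**The case against.** The strongest reply is that the safeguards already exist. Distribution is need-to-know, early analyses must not compromise safety assessment, and the provision only permits a report. Read with goodwill, these rules already forbid sending an identifying list to someone who attributes AEs. That carries weight, but they are aims without a mechanism. The chairs are named recipients, and nothing restricts content. By contrast, SAP 11.2 places safety participant listings in reports for the SMB, which is unblinded; SAP 12 sets no such limit.

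Several stronger readings are tempting, and the documents do not support them:

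- *The listings will show IDs or arm.* No section says so. A listing is naturally read as one row per participant, and nothing requires masking, but the consequence remains conditional.
- *Pause and vaccination decisions would be biased.* At a visit 9 report all scheduled vaccinations are over. A visit 4 report would be permitted, but the SAP plans none separately: ICS and neutralizing-antibody secondary endpoints are at visit 9, and the BAMA tables compare visits 4 and 9.
- *Half a year of follow-up is exposed for everyone.* 182 days applies to the last enrollee only.
- *Section 6.3 blinds the PSRT.* It names participants and site staff. The PSRT blind is stated in the SAE-unblinding text of 11.2.3.
- *PSRT members should receive no early report at all.* That would deny the chairs the arm-level results these reports exist to provide. The problem found here is individual-level content.

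It also stands that no formal between-arm testing of AEs is planned (Protocol 6.4.3.2) and that assessors already know 8 of 9 participants received vaccine. Both reduce the practical effect.

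**Conclusion.** The concern holds as a gap in the rules for early reports. Unblinded reports may reach people who are to stay blinded, and the only defined contents include responder listings and individual plots. If those identify participants, a listed responder is a vaccinee with about 99–100% probability. The chance that an unlisted participant is placebo rises from 11% to about 20% at 50% response and about 71% at 95% response, or to 46% or 34% at 95% with 10% or 20% missing. It reaches 100% only if every vaccinee responds and no result is missing.

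At a visit 9 report the exposure is AE attribution and review over about the last 30 to 182 days of follow-up, before lag. This rests on assumed response rates, equal missingness across arms and about 5 months of accrual. The documents do not show that any early report was issued. The amendment is worth making because it is cheap and protects blinded attribution; the point does not challenge the design.

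**What to change.** Add to Protocol 6.4.5.2 and SAP 10.4.2:

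> Until the last participant's day 364 visit, immunogenicity reports distributed outside the unblinded SDMC staff and the SMB contain arm-level summaries only, with no participant listings, participant IDs or identifiable individual trajectories.

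SAP 12 should mark which tables and plots are held back until then. Sample size, assays and visits do not change. The cost is that chairs and investigators see individual-level data only after follow-up ends; they keep arm-level results for decisions about future trials.

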## 7 Selection and withdrawal of participants

Participants will be healthy, HIV-uninfected (seronegative) adults who comprehend the purpose of the study and have provided written informed consent. Volunteers will be recruited and screened; those determined to be eligible, based on the inclusion and exclusion criteria, will be enrolled in the study. Final eligibility determination will depend on information available at the time of enrollment including results of screening laboratory tests, medical history, physical examinations, and answers to self-administered and/or interview questions.

Investigators should always use good clinical judgment in considering a volunteer's overall fitness for trial participation. Some volunteers may not be appropriate for enrollment even if they meet all inclusion/exclusion criteria. Medical, psychiatric, occupational, or other conditions may make evaluation of safety and/or immunogenicity difficult, and some volunteers may be poor candidates for retention.

Determination of eligibility, taking into account all inclusion and exclusion criteria, must be made within 56 days prior to enrollment unless otherwise noted in Sections 7.1 and 7.2.

### 7.1 Inclusion criteria

#### General and Demographic Criteria

1. **Age** of 18 to 50 years
2. **Access to a participating HVTN CRS** and willingness to be followed for the planned duration of the study
3. Ability and willingness to provide **informed consent**
4. **Assessment of understanding:** volunteer demonstrates understanding of this study and completes a questionnaire prior to first vaccination with verbal demonstration of understanding of all questionnaire items initially answered incorrectly
5. **Agrees not to enroll in another study** of an investigational research agent before the last scheduled protocol clinic visit
6. **Good general health** as shown by medical history, physical exam, and screening laboratory tests

